#### 4.2 Primary Safety Endpoints

Participant baseline health, including behaviors, will be recorded at Research Visit 1 with a physical exam, baseline electrocardiogram, medical history, and concomitant medication history. Additionally, baseline health and behavior data will be captured at the Intake Visit with the Study Physician. Adverse events will also be closely monitored. These are defined by Children’s Mercy Hospital Reportable Events Research Policy and Procedures as “untoward or unfavorable occurrences in a human subject, including an abnormal sign [e.g., abnormal physical exam or laboratory finding], symptom, or disease, temporally associated with the subject’s participation in the research, whether or not considered related to the subject’s participation in the research.” Additionally, an adverse event is also defined as behaviors or symptoms that occur with increased frequency or severity as consequence of the subject’s participation in the research study.

Both types of adverse events will be documented in this study. Adverse events are reported in many ways in this study. These include but are not limited to: emails to study coordinators/clinical trial manager, phone calls on study cell phone, phone calls to ADHD Clinic or Developmental and Behavioral Clinic, reported to study physician at clinic visit, reported on Medication Side Effects questionnaires, reported at research visits when asked, or via a Cerner notification of admission to the hospital to the study physician. Additionally, adverse events will be assessed and documented at Research Visit 2, Research Visit 3, Research Visit 4, 6-week Visit, 12-week Visit, and 18-week Visit.

Adverse events will be categorized and reported to the IRB as outlined in CM Policy regarding adverse events. These events will be documented consistently, regardless of how they were reported. This includes the delegation of an individual member of the study personnel to handle all adverse event reporting. All adverse events will be recorded at all research visits and in between visits as needed on the Adverse Event CRF kept in the subject’s study binder.

In addition, subjects will be classified based on their tolerance of ATX. A participant is considered tolerant of ATX if the side effects did not lead to discontinuation of ATX therapy. A participant is considered intolerant of ATX if the side effects lead to the discontinuation of medication and withdrawal of a subject from the study.

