18-Week Visit with Study Physician – The participant and family meet with a study physician approximately 6 weeks after the 12-Week Visit with Study Physician. A ± 2-week window is allowed for ease of scheduling. Prior to this visit, questionnaires will be sent out via CHADIS to parents and teachers to assess participant's behavior. During this visit, safety, efficacy, and side effects will be assessed and dose adjustments will be made accordingly. In addition, baseline questionnaires will be re-administered to gauge symptom and impairment changes post-treatment initiation. Dose adjustments may be outside research and visits with study physicians as needed.

Research Visit 4 – This visit is also referred to as pharmacokinetic study 3 (PK3) or end of study PK. This vist occurs after the 18-Week Visit with Study Physician. This visit takes place in the PCRU and consists of the same procedures as Research Visit 3. Determination of Study Design will be confirmed prior to visit, as some participants may require switching to a different study design if frequency of dosing has changed. During this visit, baseline psychometric measures will be re-administered to measure change post-treatment initiation. An end of study EKG will be obtained, and a Dietary Survey Questionnaire will be administered.

- Description of Research Procedures

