### *Prior to Visit*

- a. Optional: Obtain a signed and dated prescription from a Study Physician for topical lidocaine (either J-tip or cream) to alleviate pain with needlestick for participant.
- b. Submit signed and dated prescription to Children's Mercy Hospital Investigation Drug Services (IDS) pharmacy.
- c. Confirm participation in Study Design 1, Study Design 2, or need to switch to Study Design 3.
- d. If participant will be changing to Study Design 3, discuss with participant and/or family changes from Study Design 2.

- e. Contact participant and participant's family between 8-10 days prior to Research Visit 3 to remind participant to take all prescribed doses the week prior to Research Visit 3.
- f. Contact participant and participant's family 1 -2 days prior to the visit to:
  - i. Remind them of their scheduled visit.
  - ii. Ensure that participant has been compliant on medication for 1 week prior to scheduled Research Visit 3.
    - i. If the participant has not been compliant, the visit will need to rescheduled.
  - iii. Instruct participant to begin fasting at midnight prior to the visit. Water is permissible while fasting.
  - iv. Remind participant to bring their home atomoxetine medication to the PCRU, but to not take the medication in the morning.
  - v. Remind participant to bring U54 Study Booklet, which contains the participant's medication calendar.
  - vi. If participant has been switched to evening dosing of ATX, schedule Research Visit 3 to mirror how the participant typically takes their medication. (i.e. if the participant takes their medication in the evening, the beginning of their pharmacokinetic study should also be in the evening).
  - vii. The research team will ensure that the participant and their family are aware of the safety measures at Children's Mercy Hospital to prevent transmission of the SARS-CoV-2 virus. These resources and information to be shared will be detailed on the Children's Mercy Hospital homepage and any PCRU guidance in response to COVID-19.

*On Day of Visit*

- a. Confirm participant's willingness to continue in the research study.
- b. Obtain medication history and concomitant medications. Add to Concomitant and Prior Medications Log.
- c. Verify medication calendar with remaining capsules count.
- d. Make copies of pages in medication calendar.
- e. Measure vital signs: height, weight, blood pressure, heart rate, respiration rate, and temperature.
- f. Perform physical exam.

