    - x.* Administer end of study psychometric questionnaires:
      - i.* Screen for Child Anxiety Related Disorders (SCARED parent and participants  $\geq$  8 years old informant).

- ii.* Barkley's Sluggish Cognitive Tempo (SCT) (parent informant).
    - iii.* Behavior Rating Inventory of Executive Function (BRIEF) (parent informant. Teacher informant is optional).
  - y.* Administer Dietary Survey Questionnaire (participant informant).
- z.* Please note that the SCARED and the BRIEF are validated tools that are used to aid the Study Physician in determining treatment response. Use of different versions of these questionnaires are permissible to aid the Study Physician, in addition to clinical impression, with medication management and determination of response.
  - aa.* Assess for adverse events. Document in Adverse Events log.
  - bb.* Determine and document participant's adherence to ATX medication regimen.
    - i.* High adherence is defined as the participant taking  $\geq$  80% of their scheduled doses
    - ii.* Medium adherence is defined as the participant taking between 40 – 79% of their scheduled doses.
    - iii.* Low adherence is defined as a participant taking  $<$  40% of their scheduled doses.

11.1.1.1 Add compensation to participant's Greenphire account.

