## 20.0 Data Management

### 20.1 Data Analysis Plan

#### Population to be Analyzed:

- The pharmacokinetic population will consist of all participants with sufficient plasma concentrations for calculation of all pharmacokinetic parameters.
- The pharmacodynamic population will comprise of all patients with sufficient DHPG plasma concentrations, adequate data from pupil dilation and eye-tracking measurements, and cardiovascular measures (heart rate and blood pressure). Additional metabolites analyzed via metabolomics platform will also be analyzed (as discussed below).
- All participants who meet criteria for determination of both pharmacokinetic and pharmacodynamic parameters and have at least partially completed the study will be evaluated for pharmacodynamic linked clinical outcomes analysis. A partial completion is any participant where at least Research Visit 1, Research Visit 2, Research Visit 3, Intake Visit with Physician, and 6-week Visit with Study Physician have been completed. Clinical outcomes will be analyzed in four ways:
  - Response: responder vs. non-responder
  - Toxicity: tolerant vs. non-tolerant
  - Adherence: low, medium, and high
  - Adverse event reporting
- In addition, all participants for which demographic and background characteristics and concomitant medication history were collected will be analyzed.
- All completed and returned U54 Study Booklet questionnaires and surveys will be used to assess the effectiveness of the U54 Study Booklet in study comprehension. Feedback from the survey will be compiled for analysis.

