#### Pupillometry Analysis:

Changes in performance during Posner Cuing Task will be measured as a function ATX exposure and  $C_{max}$  concentrations. Pupil size will be measured during two types of activities: localization and discrimination tasks. Pupil size differences during localization tasks report on the individuals' baseline (tonic) release of norepinephrine. This corresponds to endogenous, or volitional attention. Pupil size differences during discrimination tasks is a composite of the individuals' baseline (tonic) and situational (phasic) release of norepinephrine. Currently it is unclear whether tonic, phasic, or both are impaired in individuals with ADHD.

Cardiovascular Marker Analysis:

Changes in heart rate will also be measured as a function ATX exposure and  $C_{max}$  concentrations. One side effect of ATX that is directly related to the pharmacodynamics of the drug is an increased heart rate due to increased concentration of norepinephrine in blood. We would like to understand the extent of this side effect as a function of increased systemic ATX exposure and  $C_{max}$ . By studying these two components, we will be able to distinguish ATX drug action in central and peripheral nervous systems.

Pharmacodynamic Changes Correlated with change in NICHQ Vanderbilt Assessment Scales:

All changes markers of pharmacodynamic action will be correlated with whether a child is classified as a responder or non-responder; and tolerant or intolerant (see Clinical Outcomes below for details). Extent of adherence will be used as a confounding factor in both of these analyses.

Clinical Outcomes:

Determine and document participant response to ATX therapy:

- Responders will be defined as:
  - Participants, who after approximately 18 weeks of continuous treatment with ATX, demonstrate  $\geq 40\%$  reduction of baseline ADHD symptom score;
  - OR the Clinical Global Improvement rating is 1 or 2 (Very Much Improved or Much Improved).
- Non-responders will be defined as:
  - Participants, who after approximately 18 weeks of continuous treatment with ATX, demonstrate  $< 40\%$  reduction of baseline ADHD symptom score, AND the Clinical Global Improvement score  $\geq 3$ .
  - Participants who discontinue ATX prior to the planned end of study (18 weeks) due to perceived lack of efficacy despite dose escalation.

Determine and document participant tolerance of ATX therapy:

- ATX intolerant participants are:

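### Adherence is adjusted for as a confounder of marker and tolerance, but it is a post-treatment outcome that side effects and benefit can change; the planned tolerance analysis should be unadjusted

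*Combined protocol and SAP*

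**What the plan says.** Section 20.1, under the heading on PD changes correlated with change in the NICHQ Vanderbilt scales, relates all PD markers to responder status and to tolerant or intolerant status. It adds: "Extent of adherence will be used as a confounding factor in both of these analyses". It names no model, adherence variable or time window, and gives no rule for children who stop early.

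Elsewhere the plan says:

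- Section 20.1, Population to be Analyzed, lists adherence as one of four clinical outcomes, beside response, toxicity and adverse events: "Adherence: low, medium, and high".
- Section 11.2, Research Visit 4, contains the step "Determine and document participant's adherence to ATX medication regimen" and the three cut-offs (at least 80%, 40 to 79%, below 40% of scheduled doses). That visit follows the 18-week visit.
- Section 11.2, Research Visits 3 and 4, requires a compliance check covering the week before: "If the participant has not been compliant, the visit will need to rescheduled". At Research Visit 2 the first dose is given in the unit.
- Section 4.2: "A participant is considered intolerant of ATX if the side effects lead to the discontinuation of medication and withdrawal of a subject from the study". The Clinical Outcomes part of 20.1 also counts as intolerant a child whose side effects interfere significantly with daily functioning, and does not require withdrawal.

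**The concern.** A confounder of marker and outcome must influence both, or share causes with both, and must not be a result of either. Adherence over the study does not fit that description for tolerance. A child with troublesome side effects may skip or stop doses, and stopping the drug for side effects, foreseen in sections 4.2 and 16.1, is the extreme case. A child who benefits may take more. If the marker predicts benefit, adherence is a common effect of benefit and of side effects. Holding it fixed can then create a marker-tolerance association that does not exist, or distort one that does.

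This bears on the second primary objective and on Hypothesis 2, which link PD markers to clinical response. The adjusted result is the one the plan specifies, so a reader would take it as the answer.

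**Working it through.** The plan gives no figure tied to adherence, so there is none to reproduce. The check is a reading of the sections side by side, then simulations to see the direction and possible size of the bias. **Every coefficient below is an assumption.**

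**Can adherence cause the marker?** Research Visit 2 measures PD after the first dose, before any home adherence exists. Research Visits 3 and 4 are rescheduled if the preceding week was not compliant. Whole-study adherence therefore reaches the measured marker only through longer-term effects that outlast a compliant week.

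**Can tolerance and response change adherence?** Stopping for side effects is in the documents. The general statement, that side effects lower and benefit raises drug-taking, is causal reasoning and not a statement in the plan.

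**Size when the truth is no association.**

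- Marker X: standard normal.
- Response: logistic in X, log-odds 0.7 or 1.2 per SD, about 30% responders.
- Intolerance T: 20%, independent of X.
- Probability of good adherence: 0.5 + a × response − b × T.
- Fit: logistic regression of T on X, without and with adherence, in 400,000 simulated children. The unadjusted odds ratio was 0.99 to 1.00 throughout.

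| a (response) | b (side effects) | Adjusted odds ratio per SD |
|---|---|---|
| 0.35 | 0.40 | about 1.08 to 1.10 (log-odds 0.7); 1.14 to 1.15 (log-odds 1.2) |
| 0.20 | 0.20 | about 1.02 to 1.04 |
| 0.10 | 0.10 to 0.20 | about 1.00 to 1.03 |

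The false path needs both effects. With a = 0, adjustment left the odds ratio unchanged.

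**Precision for comparison.** With 96 children (the planning number after 20% attrition) and an assumed 20% intolerant, the standard error of the log odds ratio per SD near the null is about 1/√(96 × 0.2 × 0.8) = 1/√15.36 = 0.255. The 95% interval multiplies or divides the estimate by exp(1.96 × 0.255) = 1.65. Even the largest bias above is well inside that.

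**Size when there is a true association.** In a linear version the true slope on X was 0.50 for both side-effect burden and response. Adherence was driven by side effects, benefit and an unmeasured factor, and was cut into three classes. Adjustment moved the tolerance slope from 0.50 to as low as 0.44 and the response slope from 0.50 to as high as 0.55. Where side effects and benefit were given equal weight, the biases cancelled.

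**Is adherence available for children who stop early?** The three-level class is assigned at Research Visit 4 only. Adherence itself is calculated from capsule counts at Research Visit 3 and the 6-, 12- and 18-week visits (Schedule of Events; section 11.4; Appendix J). Entry to the PD-linked outcome analysis requires Research Visit 3 and the 6-week visit, so each child in it should have at least two counts. Section 16.2 keeps the data of withdrawn children.

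**The case against.** The best defence is that adherence drives exposure and response, so calling it a confounder is not baseless. The compliance check covers one week and rests on a phone call, a calendar and a capsule count. It cannot show that months of intermittent dosing leave chronic PD change untouched, and section 4.1 sets out to study neurotransmitter change with chronic use. This stands for response, where adherence has a place in a sensitivity analysis. It does not rescue the tolerance adjustment, where adherence is downstream of the outcome. It is also fair that the bias may be negligible and that 20.1 already compares PD changes between responders and non-responders without an adherence term. No tolerance counterpart to that comparison is planned.

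A reader might infer something stronger: that because the class is assigned at Research Visit 4, the adjusted tolerance model loses the intolerant children. The documents do not support this as stated. The adjustment sentence speaks of extent of adherence, not of that class; earlier counts exist; and the sentence points to the Clinical Outcomes definition in 20.1, which does not require withdrawal. The loss would arise only if the Research Visit 4 class were the covariate, and only for withdrawn children. If intolerance were also taken solely from section 4.2 ("intolerant of ATX if the side effects lead to the discontinuation of medication and withdrawal of a subject from the study"), a complete-case model would hold no intolerant child and could not be fitted.

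A reader might also infer that the adjusted response analysis loses everyone who left before Research Visit 4. Response is defined at about 18 weeks. Apart from those who stop for lack of efficacy, most earlier leavers have no response class with or without adjustment, and a child who leaves after the 18-week visit has counts to that date.

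**Conclusion.** The point holds. The plan states a rule that conditions the marker-tolerance analysis on a variable it also lists as an outcome and that intolerance itself can change. The direction of the argument rests on two causal assumptions: side effects lower adherence, and benefit raises it. The size rests wholly on how strong those effects are. The adjusted odds ratio runs from about 1.00 to 1.15 per SD when the truth is 1.00, and in the linear illustration slopes shift by 0 to about 0.06. None of these is an estimate for this trial, and all are small beside the sampling error at the planned size. The change is worth making because the adjustment has little to gain for tolerance, can only muddy its interpretation, and is cheap to remove. For response the case is weaker, since adherence is partly a cause of it.

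**What to change.** Amend section 20.1 as follows.

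1. **Tolerance.** Make the unadjusted marker-tolerance analysis the planned one and remove adherence from it. Report adherence as the outcome it is listed as.
2. **Response.** Lead with the unadjusted responder comparison already described. Add a sensitivity analysis with percent of scheduled doses taken from first dose to the rating date, or to discontinuation if earlier, as a continuous covariate. Compute it from the capsule counts at Research Visit 3 and the 6-, 12- and 18-week visits, not from the Research Visit 4 class.
3. **Definitions.** Reconcile the definitions of intolerance in section 4.2 and in the Clinical Outcomes part of 20.1, so that it is clear which children the tolerance analysis counts.

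The cost is SAP wording; the counts are already planned and recorded in the adherence workbook. The downsides should be stated: the response sensitivity estimate may still carry some mediator or collider bias, and the unadjusted results do not separate non-response caused by poor drug-taking.

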ψThese visits will occur at either the ADHD Clinic on College Boulevard or in the Developmental and Behavioral Sciences Clinic. If these visits are telehealth visits, all in-person procedures, such as obtaining vitals or a physical exam, may be omitted.

This visit can occur in two parts to minimize time of washout.

€The window for this visit is flexible and has been expanded from the previous versions of this protocol. This visit can occur anytime after the participant has been taking medication regularly for 2 weeks and up until prior to the 18-Week Visit with Study Physician.

○ Procedures to Reduce Risks

1. Medical Chart Review during Prescreen will be used to determine if a potential participant has any of the following:
  - a. Diagnosis or indication of underlying risk for cardiotoxicity, such as presentation of structural cardiac abnormalities, cardiomyopathy, or arrhythmias.
  - b. Diagnosis or indication of disease that may cause abnormal absorption or gastric emptying.
  - c. Previous history or indication of prior adverse drug reaction to atomoxetine
  - d. Concurrent therapy with drugs known to inhibit CYP2D6 or previous treatment with strong CYP2D6 inhibitors.
  - e. Concurrent therapy with other psychiatric/behavioral drugs
2. The two parts of Research Visit 1 may occur at separate times for participants who require a washout prior to beginning atomoxetine therapy. Research Visit 1 Part 1 includes a blood stick for genotyping purposes. Genotyping analysis, which takes approximately one week to complete and interpret, will be conducted while the participant is washing out. Were we to collect genotyping sample when the participant is at baseline, the participant could potentially be off of medication for ~ 2 weeks, while waiting for genotyping results such that ATX can be dosed in the participant using the iGO-PK model.
3. Needlestic comfort and pill-swallowing ability questions will be asked to reduce discomfort and anxiety associated with needlessticks and taking the study drug.
4. Baseline electrocardiogram during Research Visit 1 to assess presence of any underlying risks for cardiotoxicity prior to starting participant on ATX.
5. End of study electrocardiogram during Research Visit 4 to assess for any cardiac injury that may have occurred while the participant was taking ATX chronically.

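### Children who stop atomoxetine early for lack of efficacy are defined as non-responders, but fall outside the only analysis set tied to the response comparison

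*Combined protocol and SAP*

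**What the plan says.** Section 20.1, Clinical Outcomes, gives two routes to non-response. One is an insufficient symptom reduction and global rating after about 18 weeks. The other covers "Participants who discontinue ATX prior to the planned end of study (18 weeks) due to perceived lack of efficacy despite dose escalation". The second route sets no minimum time on treatment.

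Section 20.1, Population to be Analyzed, defines the set for clinical outcomes as "All participants who meet criteria for determination of both pharmacokinetic and pharmacodynamic parameters and have at least partially completed the study". The first outcome listed for it is "Response: responder vs. non-responder". Partial completion is defined so: "A partial completion is any participant where at least Research Visit 1, Research Visit 2, Research Visit 3, Intake Visit with Physician", and also the 6-week visit. The PD population is "all patients with sufficient DHPG plasma concentrations, adequate data from pupil dilation and eye-tracking measurements, and cardiovascular measures", so three kinds of measurement are required jointly.

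On the timing of Research Visit 3 (RV3), the note to the Schedule of Events says: "This visit can occur anytime after the participant has been taking medication regularly for 2 weeks and up until prior to the 18-Week Visit". Section 11.2 makes RV3 a dosing visit that is rescheduled if the child has not been compliant in the week before. For the 6-week visit, 11.2 also allows earlier dose adjustment when the drug is not working.

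**The concern.** The discontinuation rule keeps treatment failures in the analysis as failures. The population definition then removes some of them, because a child who has stopped the drug cannot supply RV3. A child can be escalated, judged not to benefit and taken off drug before the required visits. That child has a response class but no place in the set where response is compared.

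The loss is selective. Stopping early for lack of efficacy leads only to the non-responder class, so every child lost this way comes from one side of the comparison. At stake are the responder versus non-responder contrasts behind Hypotheses 2 and 3: DHPG, *SLC6A2* genotype, baseline metabolites and the baseline-covariate classifier. Section 3.1 says the study's goal is to separate non-response at the drug target from inadequate exposure. Children who fail despite escalation bear directly on that question.

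**Working it through.** **1. The plan's own power figure.** Inputs from 20.2: 30% responders among completers, one-sided α = 0.05, power 80%, N = 96 or 120. Detectable difference in SD units = (1.645 + 0.842) × √(1/n₁ + 1/n₂).

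- N = 96 (28.8 vs 67.2): 0.554; noncentral t gives 0.558. The plan states 0.6.
- N = 120 (36 vs 84): 0.495; noncentral t gives 0.498. The plan states 0.5.

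Both reproduce to one decimal. The point does not rest on a numerical error.

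**2. The two rules side by side**, for a child who stops for lack of efficacy after escalation:

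| When the child stops | Class (Clinical Outcomes) | In the response set? |
|---|---|---|
| Before RV3 | Non-responder | No |
| After RV3, before the 6-week visit | Non-responder | No |
| After both, PK or PD not evaluable | Non-responder | No |
| After both, PK and PD evaluable | Non-responder | Yes |

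**3. How long the gap is open.** The 6-week visit has a ±2-week window, so it falls at 6 − 2 = 4 to 6 + 2 = 8 weeks. The Schedule of Events places it after RV3, and 11.1 puts the steady-state assessment at roughly 2 to 8 weeks. In that order the gap closes at about 4 to 8 weeks. If RV3 is delayed, as 11.1 and the Schedule note permit, it stays open until RV3 is done, at the latest just before the 18-week visit.

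**4. Which comparisons need RV3.** Under 11.2, genotyping blood and the baseline metabolomics sample come from Research Visit 1 (RV1), and pre-dose and first-dose blood from Research Visit 2 (RV2). *SLC6A2* genotype, baseline DHPG and metabolites, the baseline classifier and first-dose DHPG change therefore need nothing from RV3. Steady-state PK and PD do.

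**5. Effect on power (illustration only).** The documents do not say how many losses are early lack-of-efficacy stops. Suppose k of the 120 − 96 = 24 losses assumed in 20.2 are such stops and are restored as non-responders. The response proportion is 28.8/(96 + k), and the group sizes are 28.8 and 67.2 + k.

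| k (assumed) | N | Response proportion | Detectable difference | Power at 0.6 SD |
|---|---|---|---|---|
| 0 | 96 | 30.0% | 0.558 SD | 84.8% |
| 6 | 102 | 28.2% | 0.551 SD | 85.6% |
| 12 | 108 | 26.7% | 0.545 SD | 86.3% |
| 24 | 120 | 24.0% | 0.535 SD | 87.4% |

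Power hardly moves. What changes is who makes up the non-responder group.

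**6. Direction of bias (illustration only).** Take at face value the 45% T-allele carrier probability and the 0.23 difference in 20.2, read as carrier proportions. Non-responders in the set are then at 0.45 − 0.3 × 0.23 = 0.381, and responders at 0.381 + 0.23 = 0.611. Restore k = 12 stoppers.

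- Assumed carrier proportion 0.25 in stoppers: non-responders (67.2 × 0.381 + 12 × 0.25)/79.2 = 0.361; difference 0.250.
- Assumed 0.45: (67.2 × 0.381 + 12 × 0.45)/79.2 = 0.391; difference 0.220.

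The restricted set understates the contrast in the first case and overstates it in the second. The documents do not settle which applies.

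**The case against.** **The set has a narrower label.** It is introduced for participants who "have at least partially completed the study will be evaluated for pharmacodynamic linked clinical outcomes analysis". Section 20.1 also analyses background data from everyone who supplied them, refers to clinical response in the population studied, and 16.2 saves the data of withdrawn children. A wider set may have been intended for the genotype and baseline tests. It stands that the plan nowhere expressly bars these children from those tests. But none of these passages defines another response population, and the one that is defined leaves the children out.

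**Few children may fall in the gap.** RV3 normally precedes the 6-week visit, initial titration may be slow (5.1), and the withdrawal criterion for inadequate response in 16.1 refers to the 12- and 18-week visits. This stands, and limits the point to early stoppers and children without evaluable PK or PD. A reader might infer that treatment failures in general are removed. They are not: those who stop after both visits with evaluable data are retained.

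**The restriction has a purpose.** Sections 3.2 and 3.3 argue that non-response cannot be interpreted unless exposure is known, and 8.2 ties partial completion to steady-state data. This is a good reason to keep the restriction for steady-state analyses, and a real drawback of including early stoppers elsewhere. It does not require leaving them out of comparisons of genotype or pre-treatment measures.

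**Attrition is addressed.** Section 20.2 says weighting or imputation will be considered. That is conditional and unspecific, and the response class of these children is not missing: the plan assigns it.

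**Conclusion.** The conflict is in the text of 20.1. A child who stops for lack of efficacy before RV3 or the 6-week visit, or who lacks evaluable PK or PD, is a non-responder under one passage and outside the response set under another. This can bias the responder versus non-responder comparisons and limits them to children who stayed on drug. It should be corrected, but it does not undermine the design.

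The number of children affected and the size and direction of any bias cannot be derived from the documents. The power effect in the illustration is negligible, 0.558 to 0.535 SD even if all 24 assumed losses were early failures.

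Two stronger readings are tempting. A reader might take the gap between 160 enrolled and 120 completing as a count of lost failures and conclude that the 30% response rate is too high by a stated fraction. The documents do not support this. The 160 are enrolled and screened (8.2), enrolment precedes screening (11.1), screen failures are expected (9.4), and children also leave for intolerance, non-compliance or loss to follow-up (16.1). The 30% is a planning rate among completers, and estimating a response rate is not an objective. A reader might also infer that the exclusion must shrink the contrasts. That assumes early stoppers are the most extreme non-responders on each marker, which the plan does not show.

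**What to change.** In 20.1, name the population for each response comparison.

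- **Comparisons that need only RV1 or RV2 data** (*SLC6A2* genotype, baseline DHPG and metabolites, the baseline-covariate classifier, first-dose DHPG change): include every child dosed at RV2 who has a response class under Clinical Outcomes, including lack-of-efficacy stoppers without RV3 or the 6-week visit. The child must have the measurement being compared.
- **Analyses of steady-state measures from RV3 or Research Visit 4:** keep the partial-completion and PK/PD evaluability requirements.
- **Reporting:** give the baseline and RV2 comparisons in the partial-completer set as well, and state how many children are in one set but not the other, with reasons.

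The cost is SAP wording; no new data are needed. Denominators will differ between analyses, and early stoppers will have no steady-state PK to confirm their exposure. Both should be stated with the results.
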